11.4.2. Baseline Characteristics

Demographics and disease-related characteristics will be summarized via counts and percentages of subjects for categorical variables, and by N, mean, median, standard deviation, minimum, maximum for continuous variables. Summaries will be performed separately by dose group and placebo subjects (all placebo subjects combined), and for all subjects combined.

11.4.3. Pharmacokinetics and Immunogenicity

To complete the PK analyses, plasma specimens will be periodically sampled relative to study drug administration and stored frozen for pGSN measurements. For the 1 dose in the SD arm and the first 2 doses in the MAD arms, blood will be drawn within 30 minutes predose, and 5-10 minutes after the end of administration, as well as 2, 8, 12 and/or 16, and 24 hours after the end of administration (± 30 minutes) for analysis of C_{max} , $T_{1/2}$, AUC_{0-8h} , and AUC_{inf} . Identical PK sampling is encouraged on Day 3 where feasible (but not required) in the multiple-dose arms.

Immunogenicity will be assessed at the last visit on Day 28 ± 2 days. Antibodies against rhu-pGSN will be assayed from frozen specimens to determine whether the investigational product induces an antibody response in recipients.

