Doses in the multiple-dose arms should be given at 24-hour (\pm 60-minute) intervals. For the one dose in the SD arm and the first 2 doses in the multiple-dose arms, blood will be drawn within 30 minutes predose, and 5-10 minutes after the end of administration, as well as 2, 8, 12 and/or 16, and 24 hours after the end of administration (\pm 30 minutes) for analysis of plasma for maximum concentration (C_{max}), time to maximum concentration (T_{max}), terminal half-life ($T_{1/2}$), area under the curve from time zero to 8 hours (AUC_{0-8}), and area under the curve from time zero to infinity (AUC_{inf}). Sampling at both the 12- and 16-hour time points is encouraged where feasible, but only one of these two times is required. Identical PK sampling is encouraged on Day 3 where feasible, but not required in the multiple-dose arms. In the multiple-dose arms, the sample at 24 hours after the prior dose must be drawn before the next dose is given and can serve as the predose sample for the next dose as long as administered within the subsequent 30 minutes.

The syringe, filter, and extension tubing should be connected after disconnecting the IV as close to the patient as possible. On Day 28, collect samples for analysis of pGSN levels and antibodies against pGSN.

Number of subjects (enrolled):

A total of 32 (6 rhu-pGSN and 2 placebo recipients per dose cohort x 4 dosing levels)

Major inclusion criteria:

1. Age ≥ 18 years

2. Gender: either
3. Informed consent obtained from subject
4. Domicile: home, assisted living, rehabilitation facility, or nursing home (as long as the prospective participant is capable of providing written informed consent)
5. Duration of infection precipitating hospitalization by history <14 days
6. Planned or actual admission to hospital with a primary diagnosis of CAP within 24 hours of presentation to the hospital
7. Primary admitting diagnosis of pneumonia supported by a compatible clinical presentation with a documented infiltrate consistent with pneumonia on chest radiograph or CT, as assessed by the admitting emergency-department (ED), clinic, or ward physician or equivalent caregiver
 - Recommended (not mandatory) guidance/discretionary criteria defining patients with CAP:
 - At least 2 symptoms: difficulty breathing, cough, production of purulent sputum, chest pain
 - At least 2 vital sign abnormalities: fever, tachycardia, tachypnea

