5.1.4. Immunogenicity Objective

- To investigate the post-treatment development of antibodies against rhu-pGSN by Day 28

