5.2.4. Immunogenicity Endpoints

- Presence of anti-rhu-pGSN antibodies at Day 28

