9. STUDY ASSESSMENTS

The procedures and assessments that will be conducted during this study are described in this section and summarized in the Schedule of Assessments ([Table 5](#) and [Table 6](#)). Detailed instructions regarding all laboratory procedures, including collection and handling of samples, will be included in the study Laboratory Manual provided by the Sponsor or its designee.

Written informed consent must be granted by each subject prior to the initiation of any study procedure or assessment (other than those considered SOC).

Table 5: Schedule of Assessments: Single-Dose Phase

Visit	Screening	Baseline/ Randomization/ Pre-Treatment	Follow-up days				Early Term/ End-of- Study Visit
			2	3 or 4	7 ± 1	14 ± 2	
Day	-1 to 0	1^h					28 ± 4
Informed consent	X						
Eligibility assessment	X						
Medical history/signs and symptoms	X	X ⁱ					
Sputum culture ^a	X						
Blood or urine pregnancy	X (for women of childbearing potential only)						X
Hepatitis B and C, HIV	Not required (could be done at the discretion of caregivers)						
Confirmation of CAP (CXR or CT)	X						
PSI score	X		X	X			X
SOFA score	X		X	X			X
CURB-65 score	X		X	X			X
Physical exam	X	X ⁱ	X	X			X
MMSE (Abbreviated Mental Test Score)	X	X ⁱ	X	X			X
Vital signs, including pulse oximetry ^b	X	X	X	X			X

Visit	Screening	Baseline/ Randomization/ Pre-Treatment	Follow-up days				Early Term/ End-of- Study Visit
			2	3 or 4	7 ± 1	14 ± 2	
Day	-1 to 0	1 ^h	2	3 or 4	7 ± 1	14 ± 2	28 ± 4
EKG ^c	X	X ⁱ					X
PK sampling for pGSN levels ^d		X	X				
CBC with differential and reticulocyte count; PT/PTT	X	X ⁱ	X	X	X	X	X
Comprehensive metabolic profile (including amylase or lipase)	X	X ⁱ	X	X	X	X	X
Biomarker sampling ^e		X	X	X	X	X	X
Anti-rhu-pGSN antibody sampling (immunogenicity) ^f							X
Study drug administration ^g		X					
AEs		X	X	X	X	X	X
Con meds	X	X	X	X	X	X	X

Abbreviations: AEs=adverse events; CAP=community-acquired pneumonia; CBC=complete blood count; Con meds=concomitant medications; CT=computed tomography; CURB-65=Confusion, Urea >7 mmol/L, Respiratory rate ≥30/min, Blood pressure systolic <90 or diastolic ≤60, and age ≥65 years (score); CXR=chest x-ray; EKG=electrocardiogram; HIV=human immunodeficiency virus; MMSE= mini-mental state examination; PD=pharmacodynamic; PK=pharmacokinetic; PSI=pneumonia severity index; PT=prothrombin time; PTT=partial thromboplastin time; SOFA= sequential organ failure assessment (score); Term=termination.

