### 3. STATISTICAL CONSIDERATIONS

Data will be handled and processed per the sponsor's representative (Novotech) Standard Operating Procedures (SOPs), which are written based on the principles of good clinical practice (GCP).

All data collected on the eCRFs will be presented in the data listings and will be listed and sorted by SD/MAD, treatment, subject number and visit, where applicable. All summaries will present the data by SD/MAD (apart from PK summaries), treatment group and overall (total subjects), as applicable. In addition, all placebo subjects will be combined into a single placebo group for purposes of summarizing the data.

- Continuous variables: Descriptive statistics will include the number of non-missing values (N), mean, standard deviation (SD\*), median, minimum, maximum.  
  
The minimum and maximum values will be displayed to the same decimal precision as the source data, the arithmetic mean, SD\* and median values will be displayed to one more decimal than the source data for the specific variable.  
  
The appropriate precision for derived variables will be determined based on the precision of the data on which the derivations are based, and statistics will be presented in accordance with the abovementioned rules.
- PK data: For PK data the arithmetic mean, standard deviation, median, minimum, maximum, coefficient of variation (CV%), geometric mean and geometric coefficient of variation (geo CV%) values will be presented. For the ratio of concentration data to the (within 30 minutes) pre-dose concentration on Day 1, the  $\ln(\text{SD}^*)$  will also be presented.
- Categorical variables: Descriptive statistics will include frequency counts and percentages per category. Percentages will be rounded to one decimal place, with the denominator being the number of subjects in the relevant population with non-missing data, unless otherwise specified.
- Time to Event Analysis: Through the Kaplan-Meier method, nonparametric estimates of the survivor function will be represented by quartile estimates (Q1, Median and Q3) along with 95 CIs. Product limit estimates will be presented as part of appendices to the study outputs (SAS output).
- Imputation: No missing data will be imputed.
- Baseline: Baseline values will be defined as the last valid, non-missing observation for each subject prior to the first dose of study medication. For the PK analysis, baseline will be defined as the pre-dose value for each study day.

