## **12. IMMUNOGENICITY ENDPOINTS**

All Immunogenicity endpoints will be listed using the safety population by study part and treatment. Specimens from placebo recipients will serve as a negative control.

Antibodies against rhu-pGSN will be blindly assayed from frozen specimens to determine whether the investigational product induces an antibody response in recipients.

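### Antibodies are sampled only at Day 28 or early termination and no baseline result is planned, so a subject's positive cannot be classed as new or pre-existing

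*Protocol*

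**What the plan says.** The immunogenicity objective (Protocol 5.1.4) describes a change over time: "To investigate the post-treatment development of antibodies against rhu-pGSN by Day 28". Protocol 11.4.3 and SAP 12 add a causal aim. In the protocol's words, antibodies are "assayed from frozen specimens to determine whether the investigational product induces an antibody response in recipients".

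The endpoint (Protocol 5.2.4) is a single snapshot: "Presence of anti-rhu-pGSN antibodies at Day 28". The synopsis agrees: "On Day 28, collect samples for analysis of pGSN levels and antibodies against pGSN". Tables 5 and 6 each mark antibody sampling once, in the early-termination/end-of-study column, with nothing at screening or Day 1.

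SAP 12 supplies the control: "Specimens from placebo recipients will serve as a negative control". It also blinds the laboratory: "Antibodies against rhu-pGSN will be blindly assayed from frozen specimens". Results are to be listed by study part and treatment. SAP Section 17 has no antibody table, and neither document gives a rule for separating new from pre-existing antibodies.

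A serum and plasma aliquot is drawn before the first dose on Day 1 and frozen for biomarkers (Protocol synopsis; Section 9.4; Table 5 footnotes e and h; Table 6 footnotes f and j). The list of biomarkers is open-ended but does not name antibodies.

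**The concern.** The aim is development or induction, while the measurement is presence at one time point. A positive at Day 28 could be new since dosing or could have been there at admission, and the planned data do not separate the two for any one subject.

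This matters most in the likeliest awkward result: a few positives among the 24 active subjects and none on placebo. Pre-existing antibodies could then be read as a response to the product, and so few controls would not rule that out. The available text gives no background rate for these patients. Protocol 4.4.2 reports that no antibodies formed in 24 healthy volunteers after nebulized dosing, which does not supply one for hospitalized patients dosed intravenously.

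**Working it through.** **Inputs.** Protocol 7.1: 6 active and 2 placebo subjects per cohort, 4 cohorts. SAP 2.1: one single-dose (SD) cohort and three multiple-dose (MAD) cohorts. The documents give no immunogenicity sample size, error rate or background prevalence.

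**Group sizes.** Active 6 × 4 = 24; placebo 2 × 4 = 8, which reproduces the pooled placebo figure in Protocol Table 7. SAP 12 lists antibodies by study part, so placebo divides into 2 × 1 = 2 (SD) and 2 × 3 = 6 (MAD). Eight is therefore a maximum, reached only if the parts are pooled and every placebo subject provides a specimen.

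**What zero placebo positives would exclude.** The one-sided 90% upper bound for 0/n is 1 − 0.10^(1/n):

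- n = 8: 1 − 0.10^(1/8) = 25.0%
- n = 6: 1 − 0.10^(1/6) = 31.9%
- n = 2: 1 − 0.10^(1/2) = 68.4%

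Protocol Table 7 uses the same zero-event logic. Its 32% for n = 6 agrees with this formula. Its 21% for n = 8 does not: at a true rate of 21%, the chance of at least one event in 8 is 1 − 0.79^8 = 84.8%, not 90%. I therefore use 25%.

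**How often a clean placebo group would accompany a pre-existing positive on active.** Assume that a fraction b of subjects has a pre-existing antibody, equally in both groups, with a perfect assay, no induction, and all 32 subjects sampled. Then

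P(0/8 placebo and at least 1/24 active) = (1 − b)^8 × [1 − (1 − b)^24].

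| Assumed b | P(0/8 placebo) | P(at least 1/24 active) | Both | Expected among 24 active (24b) |
|---|---|---|---|---|
| 1% | 0.923 | 0.214 | 20% | 0.24 |
| 5% | 0.663 | 0.708 | 47% | 1.2 |
| 10% | 0.430 | 0.920 | 40% | 2.4 |
| 25% | 0.100 | 0.999 | 10% | 6.0 |

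The joint probability is not monotone in b. Writing x = (1 − b)^8, it equals x − x^4, which is largest at x = 0.63. That is b of about 5.6%, with a value of about 47%. The 5% row is therefore close to the worst case and is not a typical one.

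**The case against.** The strongest reply is that the trial already has the right control. Placebo is randomized and assayed blind, so a comparison of groups addresses whether the product induces antibodies without any baseline. That stands for the group question. It does not classify an individual, and the control is small. SAP 3 does say that "all placebo subjects will be combined into a single placebo group for purposes of summarizing the data", but that governs summaries. Antibodies are only listed, so the pooled contrast is not a planned display.

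A second reply is that the specification is still open. The SD antibody listing shell awaits a data transfer agreement, and the MAD shell asks for all time points. Neither note adds a baseline sample to a schedule that has none. The Laboratory Manual was not available for this review.

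Third, the prevalences are assumptions, and Protocol 4.3 describes the product as identical to an abundant natural protein, which bears on which rates are plausible. This is fair: at 1% only 0.24 pre-existing positives are expected among active subjects, and at 25% placebo would reveal the background about 90% of the time. The documents do not settle where in that range the truth lies.

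A reader might go further and infer that the induction question cannot be answered at all, or that no baseline material exists. The documents support neither reading: the placebo control is valid, and a pre-dose aliquot is frozen, so classification is unplanned, not impossible. Nor can it be said that the inhaled study is the only human antibody evidence. The text available for this review breaks off after the cohort list of the earlier intravenous study in Section 4.4.2, so nothing is claimed about its results.

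**Conclusion.** The gap is real. The objective concerns antibodies that develop after treatment; the plan measures presence once, at the end, and gives no means of classing a subject's positive as new or pre-existing. The placebo group is a sound but thin safeguard: a clean result leaves background rates of up to 25% (pooled), 32% (MAD) or 68% (SD) not excluded at one-sided 90% confidence. Over assumed pre-existing rates of 1% to 25%, the chance that a clean pooled placebo group sits beside at least one pre-existing positive on active ranges from 10% to 47%.

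The bounds rest on the planned numbers and complete Day 28 sampling. The joint probabilities also rest on the assumed rates, equal in both groups, and a perfect assay. The primary safety aim is unaffected. This is an inexpensive improvement to a descriptive endpoint, worth making because it lets the trial answer the question it sets.

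**What to change.** In Protocol 11.4.3 and SAP 12, pre-specify that:

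- for every Day 28 positive, active or placebo, the frozen Day 1 pre-dose aliquot is assayed blinded in the same run, where consent and remaining volume allow;
- where they do not, an antibody tube is added to the existing Day 1 pre-dose draw for subjects not yet dosed, with Tables 5 and 6 and the synopsis updated;
- negative at Day 1 and positive at Day 28 is classed as treatment-emergent;
- counts are tabulated by dose group and pooled placebo, and the placebo comparison is kept for attributing new antibodies to the product.

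The paired result shows whether an antibody is new; placebo is still needed to say why.

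**Cost.** At planned enrolment, at most 32 extra Day 1 assays, plus a repeat of each Day 28 positive so that the pair shares a run; one table; a line in the Laboratory Manual. Some biomarker aliquot volume is used. A protocol amendment is needed, with ethics approval and regulatory submission (Protocol 13.2 and 13.3) and possibly updated consent (13.5). The fallback tube cannot help subjects already dosed. No new visit is required.

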11.4.4. Pharmacodynamics

Biomarker and clinical outcomes will be summarized via counts and percentages of subjects for categorical variables, and by summary statistics (N, mean, median, standard deviation, minimum, maximum, 90% confidence intervals, etc.) for baseline, each observed time point, and change from baseline at each observed time point for continuous variables. Data will be assessed via graphical and Shapiro-Wilk statistic for closeness to normal distribution and if substantial departure is observed, transformation (e.g., natural log, reciprocal, square root, ranks) may be employed to derive the summary statistics.

12. DATA RECORDING, RETENTION AND MONITORING

12.1. Case Report Forms

Data will be collected using an electronic data capture (EDC) system at the clinical site. The Investigator or designee will record data specified in the protocol using eCRFs. Changes or corrections to eCRFs will be made by the Investigator or an authorized member of the study staff according to the policies and procedures at the site and the eCRF completion guidelines.

It is the responsibility of the Investigator to ensure eCRFs are complete and accurate. Following review and approval, the Investigator or designee will electronically sign and date the pages. This signature certifies that the Investigator has thoroughly reviewed and confirmed all data on the eCRF. Regardless of whether this responsibility has been delegated, the Investigator is personally responsible for the accuracy and completeness of all data included in the eCRF.

The Sponsor or designee will provide a portable document format (PDF) file of the eCRFs to the site for archiving after all data have been monitored and reconciled.

12.2. Records Retention

Per Good Clinical Practice (GCP) guidelines regarding records retention, study documents are to be retained at the site until at least 2 years after the last approval of a marketing application in an International Council for Harmonization of Technical Requirements for Pharmaceuticals for Human Use (ICH) region or at least 2 years have elapsed since the formal discontinuation of clinical development of study drug. The Sponsor will notify the site of the date when study documentation may be destroyed.

12.3. Data Monitoring

This study will be closely monitored by representatives of the Sponsor throughout its duration. Monitoring will include personal visits with the Investigator and study staff as well as appropriate communications by telephone, fax, mail, email or use of the EDC system, if applicable. It is the responsibility of the monitor to inspect eCRFs at regular intervals throughout the study to verify the completeness, accuracy and consistency of the data and to confirm adherence to the study protocol and to GCP guidelines. The Investigator agrees to cooperate with the monitor to ensure that any problems detected during the course of this study are resolved promptly. The Investigator and site will permit study-related monitoring, audits, IEC review and regulatory inspection, including direct access to source documents.

It is understood that study monitors and any other personnel authorized by the Sponsor and/or Sponsor representatives may contact and visit the Investigator and will be permitted to inspect all study records (including eCRFs and other pertinent data) on request, provided that subject confidentiality is maintained and that the inspection is conducted in accordance with local regulations.

Every effort will be made to maintain the anonymity and confidentiality of subjects during this study. However, because of the experimental nature of this treatment, the Investigator agrees to allow representatives of the Sponsor as well as authorized representatives of regulatory authorities to inspect the facilities used in the conduct of this study and to inspect, for purposes of verification, the hospital or clinic records of all subjects enrolled in the study.

12.4. Quality Control and Quality Assurance

The study site may be audited by a quality assurance representative of the Sponsor or its designee for the purpose of monitoring any aspect of the study. The Investigator agrees to allow the monitor and/or auditor to inspect the drug storage area, study drug stocks, drug accountability records, patient charts and study source documents, and other records relative to study conduct.

The Investigator should contact the Sponsor or designee immediately if contacted by a regulatory agency about an inspection.

13. REGULATORY, ETHICAL AND LEGAL OBLIGATIONS

13.1. Good Clinical Practice

The study will be performed in accordance with the protocol, guidelines for GCP established by the ICH, and applicable local regulatory requirements and laws.

13.2. Independent Ethics Committee Approval

The Investigator must inform and obtain approval from the IEC for the conduct of the study at named sites, the protocol, informed consent documents and any other written information that will be provided to the subjects and any advertisements that will be used. Written approval must be obtained prior to recruitment of subjects into the study and shipment of study drug.

The Investigator is responsible for informing the IEC of any amendment to the protocol in accordance with local requirements. Amendments may be implemented only after a copy of the approval letter from the IEC has been transmitted to the Sponsor. Amendments that are intended to eliminate an apparent immediate hazard to subjects may be implemented prior to receiving Sponsor or IEC approval. However, in this case, approval must be obtained as soon as possible after implementation.

Per GCP guidelines, the Investigator will be responsible for ensuring that an annual update is provided to the IEC to facilitate continuing review of the study and that the IEC is informed about the end of the study. Copies of the update, subsequent approvals and final letter must be sent to the Sponsor.

13.3. Regulatory Authority Approval

The study will be performed in accordance with regional regulatory requirements and will also meet all of the requirements of ICH GCP guidance. Amendments to the protocol will be submitted to the appropriate regulatory agency/agencies prior to implementation in accordance with applicable regulations.

13.4. Other Required Approvals

In addition to IEC and regulatory authority approval, all other required approvals (e.g. approval from the local research and development board or scientific committee) will be obtained prior to recruitment of subjects into the study and shipment of study drug.

13.5. Informed Consent

It is the responsibility of the Investigator (or designee) to obtain written informed consent from each subject after adequate explanation of the aims, methods and potential hazards of the study and before any study procedures are initiated. The subject should be given the opportunity to ask questions and allowed time to consider the information provided. Each subject should be given a copy of the informed consent document and associated materials. The original copy of the signed and dated informed consent document must be retained at the site and is subject to inspection by representatives of the Sponsor or regulatory authorities; the subject should be given a copy of the signed ICF.

Substantial changes to the study protocol may necessitate modifications to the informed consent document. If an amended informed consent document is issued during a subject's participation in the study, the subject is required to provide written informed consent using the updated consent form prior to continuing with study-related activities.

Subjects unable or unwilling to provide written informed consent will not be enrolled in the study.

